## **c. Study Rationale**

The clinical benefits of Entresto are widely accepted, but there are many pathways through which these benefits may be derived. The increase in circulating natriuretic peptides are considered to decrease myocardial apoptosis and ventricular remodeling and to oppose other systemic effects of adverse activation of the renin-angiotensin and sympathetic nervous systems. The natriuretic peptides also have direct hemodynamic effects on sodium and water excretion and on vascular tone. These effects could lead to reduction in elevated pulmonary artery pressures, which are associated with many of the symptoms of HF and with the development of pulmonary hypertension which impairs right heart function and contributes to development of secondary right heart failure.

This pilot study takes advantage of the availability of the home monitoring device for HF management, and will include only patients in whom this device has already been implanted for management according to clinical indications. It will test the primary hypothesis that the

replacing ACEI/ARB therapy with Entresto will lower pulmonary artery pressure at 6 weeks compared to continuation of ACE inhibitor/ARB therapy and that that improvement will be sustained over the course of 20 additional weeks of therapy. In addition, the immediate first-dose response will be assessed on the first day of administration, with the hypothesis that the first dose will lead to immediate reduction in pulmonary artery pressures. The durability of the effect will be assessed over the next 20 weeks during the longitudinal phase, with the hypothesis that early reductions in pulmonary artery pressure will be sustained.

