## Statistical Analysis

### Co-Primary Endpoints:

#### *Intensive Phase:*

- *Determine the difference between mean change in mean pulmonary artery pressure (PAPm) after 6 weeks on Entresto compared to 6 weeks on continued ACEi/ARB*
  - *Statistical Plan: These changes from baseline to 6 weeks constitute continuous data. Therefore, the distribution of average changes in PAPm from baseline to 6 weeks will be assessed in Group A and Group B. If both distributions are normal, t-testing will be performed to compare the mean changes between groups. If the distributions are not normal, Wilcoxon testing will be used. P <0.05 will be significant.*

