### Secondary Endpoints:

- *Determine the mean change in PAPm in both groups on Entresto from week 12 to week 32 in longitudinal study*
  - *Statistical Plan: The changes in PAPm from week 12 to week 32 constitute continuous data. The distribution of average change in PAPm from week 8 to week 32 will be assessed in both group A and B. The distribution of changes in*

PAPm will be assessed for normality. If the distributions are normal, the results will be presented as means with standard errors. If the distributions are not normal, the results will be presented as medians with interquartile ranges.

- *Determine the difference between mean change in PAPm from baseline on ACEI/ARB to 6 weeks on Entresto (Groups A and B)*
  - Statistical Plan: The distribution of the average change in PAPm from baseline to 6 weeks will be assessed in Group A and combined with the distribution of change in PAPm from week 6 to week 12 in Group B. The combined distributions will be assessed for normality. If the combined distribution of changes in PAPm is normal, the results will be presented as means with standard errors. If the distributions are not normal, the results will be presented as medians with interquartile ranges.
  
- *Determine the impact of therapy over time on standard 6 minute walk test, assessing distance walked and changes in PAPm during recovery after the walk.*
  - Statistical Plan: These changes in distance walked from baseline to 6 weeks constitute continuous data. Therefore, the distribution of average changes in PAPm from baseline to 6 weeks will be assessed in Group A and Group B. If both distributions are normal, t-testing will be performed to compare the mean changes between groups. If the distributions are not normal, Wilcoxon testing will be used.  $P < 0.05$  will be significant.

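### The PAPm durability analysis starts at week 12, so week 32 is never compared with the ACEi/ARB value and, for Group A, any loss between weeks 6 and 12 is missed

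*Combined protocol and SAP*

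**What the plan says.** Section I.c (Study Rationale) expects a lower PAPm at 6 weeks than on continued ACEi/ARB, and then "that improvement will be sustained over the course of 20 additional weeks of therapy". It repeats the durability aim for the longitudinal phase, "with the hypothesis that early reductions in pulmonary artery pressure will be sustained".

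The Statistical Analysis text in section VI has three resting-PAPm analyses that span weeks rather than hours:

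- **Co-primary (Intensive Phase).** "average changes in PAPm from baseline to 6 weeks will be assessed in Group A and Group B", and the two groups are then compared.
- **6-week own-control secondary.** Group A's change from baseline to week 6 is "combined with the distribution of change in PAPm from week 6 to week 12 in Group B".
- **Longitudinal secondary.** The title is "Determine the mean change in PAPm in both groups on Entresto from week 12 to week 32 in longitudinal study". The plan text beneath it gives another start: "The distribution of average change in PAPm from week 8 to week 32 will be assessed in both group A and B".

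The longitudinal result is descriptive: "If the distributions are normal, the results will be presented as means with standard errors", otherwise medians with interquartile ranges. There is no test, no margin and no statement of what would count as sustained.

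**The concern.** To say that a reduction has lasted, one needs the level before the reduction, or the level at which it was first shown. The longitudinal secondary uses neither for Group A. That group's effect is fixed at week 6 and its durability is measured from week 12, so with the titled start date its weeks 6 to 12 on Entresto enter no resting-PAPm analysis. In neither group is week 32 set against the ACEi/ARB value.

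Section VIII.b (Potential Benefits to Society) says that a sustained fall in PA pressures would be the basis for a further trial on right-sided heart failure. The planned results would not directly support or refute that.

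**Working it through.** **1. The plan's own figure.** Power Analysis: 10 per group, a difference of 20% of 25 = 5 mm Hg, SD 3.4, two-sided alpha 0.05. Standard error = 3.4 × √(2/10) = 1.52; 5/1.52 = 3.29; 3.29 − 1.96 = 1.33; power = Φ(1.33) = 0.908. The stated 90% is reproduced by the normal approximation (the noncentral t gives 87.5%; that is a separate, small matter). The figure is for week 6. The documents give no power or precision for weeks 12 to 32.

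**2. Time on drug at week 12.** Section VIII.a gives 32 weeks of Entresto for Group A and 26 for Group B by study end. Twenty weeks earlier, at week 12, that is 32 − 20 = 12 weeks for A and 26 − 20 = 6 weeks for B. Week 12 is therefore the 6-week Entresto point for B but not for A.

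**3. Assumed PAPm paths.** These use the Power Analysis values of 25 and 20 mm Hg at baseline, week 6, week 12 and week 32. Contrast (a) is week 32 minus the last ACEi/ARB value (A: baseline; B: week 6). Contrast (b) is week 32 minus the 6-week Entresto value (A: week 6; B: week 12). The last three columns give A / B / pooled.

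| Case | Group A | Group B | Co-primary | 6-week secondary | Planned wk 12–32 | (a) | (b) |
|---|---|---|---|---|---|---|---|
| Fall kept | 25, 20, 20, 20 | 25, 25, 20, 20 | −5 | −5 | 0 / 0 / 0 | −5 / −5 / −5 | 0 / 0 / 0 |
| Lost by 12 weeks on drug, both groups | 25, 20, 25, 25 | 25, 25, 20, 25 | −5 | −5 | 0 / +5 / +2.5 | 0 / 0 / 0 | +5 / +5 / +5 |
| Lost in A only | 25, 20, 25, 25 | 25, 25, 20, 20 | −5 | −5 | 0 / 0 / 0 | 0 / −5 / −2.5 | +5 / 0 / +2.5 |
| No early fall | 25 throughout | 25 throughout | 0 | 0 | 0 / 0 / 0 | 0 / 0 / 0 | 0 / 0 / 0 |

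In the second row the pooled planned change is (0 + 5)/2 = +2.5, against a true loss of 5. In the third row every planned result equals that of the first. In the fourth the planned change is 0 as well, but the co-primary and the 6-week secondary show that nothing fell. Contrasts (a) and (b) together separate all four rows.

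**4. Precision.** Half-width of the 95% CI = t(0.975, n − 1) × SD/√n. The SD of a change to week 32 is not given. I assume 3.4 to 6.8, the two SDs in the Power Analysis, with no dropout.

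- All 20 patients: 2.093 × 3.4/√20 = 1.6; 2.093 × 6.8/√20 = 3.2 mm Hg.
- Group A alone (n = 10): 2.262 × 3.4/√10 = 2.4; 2.262 × 6.8/√10 = 4.9 mm Hg.

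At SD 6.8 a pooled planned change of +2.5 has a CI of about −0.7 to +5.7, which is compatible with no loss. A kept fall of −5 in contrast (a) has a pooled CI of −8.2 to −1.8 at the same SD, which excludes zero.

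**5. The week-8 start.** Starting at week 8 would catch a Group A loss in weeks 8 to 12 but not in weeks 6 to 8. It would start Group B about 2 weeks into Entresto instead of 6, and it adds no link to ACEi/ARB. The two start weeks must be reconciled, but neither choice closes the gap.

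**The case against.** Several points on the other side are sound.

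- **A fall that never happened.** A reader might infer that a flat week 12 to 32 change would pass for a lasting effect even if there had been no early fall. The documents do not support that, since the co-primary and the 6-week secondary would both be near zero.
- **A flat result with everyone back at ACEi/ARB level.** A reader might also infer that the pooled change could be flat while both groups had lost the whole effect. If both groups held the 5 mm Hg fall at 6 weeks on drug, Group B must show +5. A pooled change of 0 then needs −5 in Group A, which means A stood 5 mm Hg above its ACEi/ARB level at week 12. The fully hidden case (third row) needs A to lose the effect while B, on the same drug, keeps it. With 10 per group chance could do this, but it is not the expected pattern.
- **Group B has an indirect link.** Its mean changes for weeks 6 to 12 and 12 to 32 add up to week 32 minus ACEi/ARB. That stands in part: the first is planned only as part of a pooled summary, medians would not add, and no interval follows from the two pieces.
- **The missing comparator.** A reader might take the rationale to promise a comparison with continued ACEi/ARB to the end. It ties that comparison to 6 weeks, so Group B's switch breaks no promise. The rationale also places durability in the longitudinal phase, and weeks 12 to 32 are 20 weeks.
- **No decision rule.** Nothing in the plan says that a flat change means sustained. That reading is an inference, though the lack of any definition is part of the gap.
- **A descriptive secondary in a 20-patient pilot.** The contrasts could be added at reporting. They could, but contrasts chosen after the data are seen carry less weight.

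**Conclusion.** The point holds for two gaps: week 32 is not compared with ACEi/ARB in either group, and Group A's week 32 is not linked to its week-6 result. With an assumed 5 mm Hg fall lost by 12 weeks on drug in both groups, the planned analysis shows none of the loss in Group A, all of it in Group B and half of it (+2.5) pooled. If results are shown by group, a split of 0 against +5 could be noticed, but the plan does not say how it would be read. The size rests on the plan's 25 and 20 mm Hg and on the assumed timing of the loss; the gaps themselves do not depend on these figures. The co-primary is unaffected. This is a cheap improvement that should be made, since it lets the trial answer its own durability question.

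**What to change.** In the Statistical Analysis text for the longitudinal PAPm secondary:

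1. Report, by group and pooled, each with a 95% CI: (a) PAPm at week 32 minus the last ACEi/ARB value (A: baseline; B: week 6); (b) PAPm at week 32 minus the 6-week Entresto value (A: week 6; B: week 12).
2. Add Group A's change from week 6 to week 12.
3. Keep the week 12 to 32 change as supporting description, and reconcile its two start weeks.
4. State in advance that any conclusion of a sustained effect rests on (a) and (b) together: the 95% CI for (a) lies below zero, and (b) shows how much of the 6-week fall is retained. Asking only that (a) remain negative would accept a trivial residual fall.

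The cost is a paragraph of analysis text and one more table. PA pressure is already recorded at every visit (section V.a) and from home on Mondays and Thursdays (section V.e), so no new data are needed.

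The downside is that (a) has no concurrent control after week 6. In Group A it may also be biased towards a fall by regression to the mean, because inclusion criterion 8 requires an average PAPm above 20 mm Hg. Label (a) accordingly and always show it by group. Group A alone gives wide intervals (half-width 2.4 to 4.9 mm Hg over the assumed SDs).

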### *Schedule of Administration*

Entresto is administered twice a day. On day 5 and day 47, patients will be instructed to hold their other morning medications and take only their first dose of Entresto and placebo or ACEi/ARB and placebo. They will then be asked to measure their PA pressures using their home CardioMEMS device 1, 2, and 3 hours after their first dose of Entresto or ACEi/ARB.

Both groups will do this on day 5 and day 47. On day 5, Group A will be measuring the first dose effect of Entresto and Group B will be measuring the first dose effect of ACEi/ARB after the washout period. On day 47, Group A will be measuring the acute effects of Entresto after 6 weeks of therapy and Group B will be measuring the first dose effects of Entresto.

Patients will also be asked to complete this “acute PA pressure measurement” schedule, i.e. holding morning medications, measuring PA pressure before and at hours 1, 2, 3 after their morning dose of Entresto or ACEi/ARB, after any dosing change.

On all other days, patients will take their morning dose of Entresto or ACEi/ARNB and placebo with their other morning medications. The evening dose of Entresto or ACEi/ARB and placebo can be taken with other evening medications as well.

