### *Secondary Endpoints:*

- The mean change in PAPm in both groups on Entresto from week 12 to week 32 in longitudinal study
- Difference between mean change in PAPm from baseline on ACEI/ARB to 6 weeks on Entresto (groups A and B)
- \*Change in exercise recovery PAPm
- \*Change PAPm, blood pressure and heart rate during isometric exercise and recovery after isometric exercise.
- Change PAPm, blood pressure and heart rate during isometric exercise and recovery after mental stress challenge.
- \*Change in NT-proBNP and the BNP/NT-proBNP ratio

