  - Statistical Plan (*Intensive Phase, patients in both groups as their own control after 6 weeks of Entresto- Group A: week 6 minus baseline; Group B: week 12 minus week 6*): The change in PAPm from pre to peak exercise at baseline and at 5 minute intervals for 30 minutes of recovery will be compared to the change in PAPm from pre to peak exercise and at 5 minute intervals for 30 minutes of recovery at 6 weeks in Group A. If the distributions are normal, the results will be presented as means with standard errors. If the distributions are not normal, the results will be presented as medians with interquartile ranges. The change in PAPm from pre to peak exercise at 6 weeks and at 5 minute intervals for 30 minutes of recovery will be compared to the change in PAPm from pre to peak exercise and at 5 minute intervals for 30 minutes of recovery at week 12 in Group B. If the distributions are normal, the results will be presented as means with standard errors. If the distributions are not normal, the results will be presented as medians with interquartile ranges.

- Statistical Plan (*Intensive Phase, patients on the Entresto Group A: week 6 minus baseline*) compared to patients on continued ACEi/ARB therapy; Group B: week 6 minus baseline): The change in PAPm from pre to peak exercise and at 5 minute intervals for 30 minutes of recovery at 6 weeks in Group A will be compared to the change in PAPm from pre to peak exercise and at 5 minute intervals for 30 minutes of recovery at 6 weeks in Group B. If both distributions are normal, t-testing will be performed to compare the mean changes between groups. If the distributions are not normal, Wilcoxon testing will be used.  $P < 0.05$  will be significant.
- Statistical Plan (*Longitudinal Phase, Patients in both groups - week 32 minus week 12*): The change in PAPm from pre to peak exercise and at 5 minute intervals for 30 minutes of recovery at 32 weeks will be compared to the change in PAPm from pre to peak exercise and at 5 minute intervals for 30 minutes of recovery at 12 weeks in both groups. If the distributions are normal, the results will be presented as means with standard errors. If the distributions are not normal, the results will be presented as medians with interquartile ranges.
- *Determine the impact of therapy over time on standard double Master's step test, assessing changes in PAPm during recovery after the test.*

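### Five secondary and exploratory analysis rules are wrong or missing as written, including a PAPm durability window that starts at week 8 instead of week 12

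*Combined protocol and SAP*

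**What the plan says.** **PAPm durability.** The secondary endpoint under Study Endpoints, matching the objective in II.a, is "The mean change in PAPm in both groups on Entresto from week 12 to week 32 in longitudinal study". The rule under Statistical Analysis opens in agreement: "The changes in PAPm from week 12 to week 32 constitute continuous data". The next sentence, which says what will be computed, reads "The distribution of average change in PAPm from week 8 to week 32 will be assessed in both group A and B". Section I.c Study Rationale adds: "The durability of the effect will be assessed over the next 20 weeks during the longitudinal phase".

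**Walk distance.** Section II.a makes change in distance walked a secondary objective and marks it for three comparisons: Group A against Group B at week 6, each patient against their own ACEi/ARB period after six weeks of Entresto, and week 12 against week 32. The rule reads "These changes in distance walked from baseline to 6 weeks constitute continuous data. Therefore, the distribution of average changes in PAPm" and continues with the baseline to week 6 change in the two groups. The three further walk bullets concern PAPm, for example "The change in PAPm from pre to peak exercise and at 5 minute intervals for 30 minutes of recovery at 32 weeks". The secondary list under Study Endpoints includes exercise-recovery PAPm but not distance.

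**KCCQ.** The tertiary endpoint is the relationship between PAPm change and change in KCCQ items 3, 7, 8 and 9. Its three rules describe or compare KCCQ change alone. The between-group rule is labelled week 6 minus baseline, but its text uses baseline to week 4.

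**BNP/NT-proBNP ratio.** The ratio appears in the objectives, in the endpoints, in the heading of its analysis rule and in the V.a visit schedule. The three rules under that heading analyse NT-proBNP only.

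**The concern.** In each case the sentence that tells the programmer what to compute does not produce the stated endpoint.

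The durability error is the one most likely to pass unnoticed. PAP is recorded at both week 8 and week 12, so the wrong window would run without a missing-data warning. Group B would then be early in its Entresto period, and part of its initial response could be counted in a result meant to show persistence.

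The walk paragraph, run literally, repeats the co-primary test and gives no distance result. The KCCQ between-group test points to a visit with no KCCQ. The PAPm-KCCQ relationship and the BNP/NT-proBNP ratio would not be estimated at all. A baseline BNP that is never drawn or recorded may not be recoverable later, so that item should be settled before data collection.

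**Working it through.** The documents give no figure to reproduce here. The check sets each endpoint beside its rule, the V.a visit schedule and the data forms.

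1. **Durability window.**
   - As written: 32 − 8 = 24 weeks. As defined: 32 − 12 = 20 weeks, which agrees with the 20 weeks in I.c. V.a ends the intensive phase at week 12 and places the longitudinal visits at weeks 18, 24 and 32.
   - Group B's exposure at week 8: V.b, Schedule of Administration, says that on day 47 "Group B will be measuring the first dose effects of Entresto". Week 8 is day 56, so 56 − 47 = 9 days. If weeks are counted from the day 5 first dose, week 8 is day 5 + 56 = 61, so 61 − 47 = 14 days.
   - How much of the response is still developing then depends on a time course that the documents do not give, so no mm Hg figure follows.

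2. **Walk distance.** The co-primary rule says "Therefore, the distribution of average changes in PAPm from baseline to 6 weeks will be assessed in Group A and Group B". The walk paragraph's operative sentence uses the same words, followed by the same choice of t-test or Wilcoxon test. By comparison:
   - A v B at week 6: distance is named in the opening sentence, but PAPm is assessed.
   - Own control: PAPm only.
   - Week 12 to 32: PAPm only.

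   So 0 of 3 comparisons has an operative sentence that uses distance.

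3. **KCCQ at week 4.** V.a schedules KCCQ at baseline and weeks 6, 12 and 32, and the endpoint-visit form adds week 24. Scheduled KCCQ observations at week 4: 0.

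4. **PAPm-KCCQ relationship.** Rules that name a correlation, regression or other association with PAPm: 0 of 3. The precision available from the planned 20 patients, using a Spearman coefficient r on the Fisher z scale with SE = √((1 + r²/2)/(n − 3)), is:
   - r = 0: SE = √(1/17) = 0.243; 95% CI −0.44 to 0.44.
   - r = 0.5: SE = √(1.125/17) = 0.257; 95% CI 0.05 to 0.78.

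   Intervals this wide support an exploratory estimate and no more.

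5. **BNP/NT-proBNP ratio.**

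| Place | NT-proBNP | BNP or ratio |
|---|---|---|
| V.a schedule: baseline, weeks 6, 12, 32 | yes | yes, 4 visits |
| V.e list, endpoint visits | yes | yes |
| V.e list, baseline | yes | no |
| Baseline form | yes | no |
| Endpoint-visit form | yes | no |
| Three analysis rules | 3 of 3 | 0 of 3 |

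6. **Wording only; no calculation changes.**
   - Two of the three NT-proBNP labels disagree with their own text. The own-control label uses weeks 4 and 8 where the text uses weeks 6 and 12. The longitudinal label starts at week 8 where the text starts at week 12. The between-group label is right.
   - Comparison 3, in II.a and Study Endpoints, describes 12 and 32 weeks on Entresto for all patients. By calendar day Group B has had (84 − 47)/7 = 5.3 and (224 − 47)/7 = 25.3 weeks. Counted from day 5 it has had (89 − 47)/7 = 6 and (229 − 47)/7 = 26, which matches the 26 weeks in VIII.a.

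**The case against.** The strongest reply is that the first three items are copying slips that the documents already resolve. The objectives, the endpoint list, the rule's heading and the sentence just before it all give week 12 for PAPm durability. The walk paragraph names distance at its start and supplies groups, window and test, so the A v B distance comparison is better called miswritten than absent. The KCCQ label says week 6, and no week 4 data exist to be analysed by mistake. The 20 weeks in I.c is also imperfect support, because that section separately speaks of 20 more weeks after the 6-week improvement. Finally, the week 12 to 32 analyses are descriptive, so no test or error rate depends on them.

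Most of this stands as an argument about weight. It does not remove the contradictions. Week 8 also appears as the start in the longitudinal NT-proBNP label, so a programmer meets it twice. Distance has no text at all for two of its three comparisons. The window in item 1 rests on the objectives, endpoint list and rule heading even without I.c. The missing association and the missing ratio are omissions that correcting a typing error cannot cure.

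Spearman is one of several acceptable choices, and the intervals above assume complete data on all 20 patients. BNP collection is planned at the endpoint visits; what is missing is the form fields, the baseline list entry and the analysis.

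**Conclusion.** The concern holds for all five items. As written, the durability window is 24 weeks instead of 20, distance walked is the operative variable in 0 of 3 comparisons, and the KCCQ between-group test uses a week with 0 scheduled observations. The PAPm-KCCQ relationship and the BNP/NT-proBNP ratio are each estimated in 0 of 3 rules, and BNP has a field on 0 of 2 forms.

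These are secondary or exploratory analyses, so this should be fixed but does not threaten the trial's main result. The co-primary analyses and sample size are unaffected. The conclusion rests on the text alone. The only assumption is how weeks are counted, which moves Group B's exposure at week 8 between 9 and 14 days.

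**What to change.** 1. In the PAPm durability rule, change week 8 to week 12.
2. In the walk paragraph, replace PAPm with distance walked. State the distance analysis for all three comparisons: A v B at week 6; own control (Group A week 6 minus baseline, Group B week 12 minus week 6); and week 32 minus week 12. Add distance to the secondary list under Study Endpoints.
3. In the KCCQ between-group rule, change week 4 to week 6.
4. Add one prespecified association: the Spearman correlation of PAPm change with change in the KCCQ item 3, 7, 8 and 9 score over the own-control six weeks of Entresto, both groups pooled, with a 95% CI and labelled exploratory. Use the same PAPm change as the own-control secondary endpoint and the single score field already on the forms, and state how that score is formed.
5. Add the BNP/NT-proBNP ratio to the three NT-proBNP contrasts. Add BNP to the V.e baseline list, the baseline form and the endpoint-visit form.
6. Align the two NT-proBNP labels with their text, and describe comparison 3 as study week 12 against study week 32.

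The cost is wording in the analysis plan and endpoint list, plus a BNP line in one list and on two forms. V.a already schedules the ratio at baseline and weeks 6, 12 and 32, so no visit is added.

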  - Statistical Plan (*Intensive Phase, patients in both groups as their own control after 6 weeks of Entresto- Group A: week 6 minus baseline; Group B: week 12 minus week 6*): The change in PAPm, blood pressure and heart rate from pre to peak isometric exercise at baseline and at 5 minute intervals for 15 minutes of recovery will be compared to the changes in PAPm, blood pressure and heart rate from pre to peak isometric exercise and at 5 minute intervals for 15 minutes of recovery at 6 weeks in Group A. If the distributions are normal, the results will be presented as means with standard errors. If the distributions are not normal, the results will be presented as medians with interquartile ranges. The change in PAPm, blood pressure and heart rate from pre to peak isometric exercise at 6 weeks and at 5 minute intervals for 15 minutes of recovery will be compared to the change in PAPm, blood pressure and heart rate from pre to peak isometric exercise and at 5 minute intervals for 15 minutes of recovery at week 12 in Group B. If the distributions are normal, the results will be presented as means with standard errors. If the distributions are not normal, the results will be presented as medians with interquartile ranges.
  - Statistical Plan (*Intensive Phase, patients on the Entresto Group A: week 6 minus baseline) compared to patients on continued ACEi/ARB therapy; Group B: week 6 minus baseline*): The change in PAPm, blood pressure and heart rate from pre to peak isometric exercise and at 5 minute intervals for 15 minutes of recovery at 6 weeks in Group A will be compared to the change in PAPm, blood pressure and heart rate from pre to peak isometric exercise and at 5 minute intervals for 15 minutes of recovery at 6 weeks in Group B. If both distributions are normal, t-testing will be performed to compare the mean changes between groups. If the distributions are not normal, Wilcoxon testing will be used.  $P < 0.05$  will be significant.
  - Statistical Plan (*Longitudinal Phase, Patients in both groups - week 32 minus week 12*): The change in PAPm, blood pressure and heart rate from pre to peak

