## Power Analysis

There will be 20 patients total, 10 in each group.

*Between group comparison:* This sample size will provide 90% power with 2-sided alpha of 0.05 to detect a 20% difference between the 2 groups (Entresto and ACEI/ARB) in the PAPm change at 6 weeks, based on an assumed baseline PAPm of 25 mm, using a t-test with a standard deviation in the mean change of as high as 3.4. We do not yet have data on which to estimate the standard deviation of this change, but we have found a standard deviation of 3-4 mm Hg of PAPm pressures during 5 day periods in stable patients followed on Cardiomems devices at Brigham and Women's Hospital (unpublished data).

*All patients after 6 weeks of Entresto compared to chronic ACEI/ARB at baseline:* There is additional power for this highest secondary endpoint. Assuming the PAPm baseline on ACEI/ARB mean of 25mm, a sample size of 20 patients will provide 90% power with two-sided alpha of 0.05 paired t-test to detect a 20% decrease (to PAPm of 20 mm) after 6 weeks of Entresto, with a standard deviation for the change as high as 6.8.

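### The week-6 between-group comparisons at peak and at each recovery time are all called significant at P < 0.05, with no recovery summary, testing order or multiplicity rule

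*Combined protocol and SAP*

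**What the plan says.** Under Statistical Analysis, Secondary Endpoints, each of the four challenge tests (6-minute walk, double Master's step, handgrip, Stroop) has a plan comparing Group A with Group B at week 6. For walk and step the quantity is "the change in PAPm from pre to peak exercise and at 5 minute intervals for 30 minutes of recovery". For handgrip and Stroop it is PAPm, blood pressure and heart rate at peak (Stroop: during the test) and every 5 minutes for 15 minutes of recovery. The method is the same each time: "If both distributions are normal, t-testing will be performed to compare the mean changes between groups", with Wilcoxon otherwise.

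The threshold set for the intensive-phase co-primary endpoint, "P <0.05 will be significant", closes each of these plans too. It also closes the between-group plans for walk distance, NT-proBNP, the four KCCQ questions and diuretic dose. The last two are headed exploratory but keep the threshold.

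The own-control and longitudinal comparisons are descriptive only (means with standard errors, or medians with interquartile ranges) and carry no threshold. On size, the Power Analysis states: "There will be 20 patients total, 10 in each group".

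**The concern.** Each patient's recovery readings form one curve, and the objective for these tests is PAPm during recovery, not PAPm at a particular minute. The plan neither reduces the curve to one quantity nor models it. On a natural reading, every time point is compared separately and may be called significant.

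In a 20-patient pilot this gives chance many opportunities. Because a patient's readings are correlated, false positives would also tend to fall at neighbouring minutes and look like a coherent effect. The section on potential benefits to society foresees a further trial building on this one, so such a result could be carried forward.

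**Working it through.** **The plan's own figure.** The documents give no number of tests and no familywise error rate. The only related figure is the power of the co-primary comparison: "This sample size will provide 90% power with 2-sided alpha of 0.05 to detect a 20% difference between the 2 groups", "based on an assumed baseline PAPm of 25 mm", with an SD of change of 3.4. The difference is 0.20 × 25 = 5 mm Hg. By normal approximation, 5 / (3.4 × √(2/10)) = 3.29 and Φ(3.29 − 1.96) = 0.908, which reproduces 90%. The exact t calculation gives 87.5%. That test is not part of the count below.

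**Number of tests, one per time point.**

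| Item | Blood pressure as one variable | Systolic and diastolic separate |
|---|---|---|
| Walk distance | 1 | 1 |
| Walk PAPm (peak + 6 recovery times) | 7 | 7 |
| Step PAPm (peak + 6) | 7 | 7 |
| Handgrip (peak + 3 recovery times) | 4 × 3 = 12 | 4 × 4 = 16 |
| Stroop (during + 3 recovery times) | 4 × 3 = 12 | 4 × 4 = 16 |
| NT-proBNP, KCCQ, diuretic dose | 3 | 3 |
| Total | 42 | 50 |

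The data collection sheets record systolic and diastolic pressure separately; the analysis text says only blood pressure. Adding the BNP/NT-proBNP ratio gives 51, and taking the four KCCQ questions singly gives 54. Recovery minutes make up 30 of 42 tests (71%) or 36 of 50 (72%).

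**Expected false positives if no test has a true effect.** This is m × 0.05, whatever the correlation: 42 × 0.05 = 2.1, 50 × 0.05 = 2.5, 54 × 0.05 = 2.7.

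**Chance of at least one.** If the tests were independent, 1 − 0.95^m gives 88% (42), 92% (50) and 94% (54). Readings within a patient are correlated, which lowers this. The documents give no correlation, so the values here are assumptions. Simulated trials with 10 per group and 50 tests gave:
- correlation 0.7 within each test and variable, none across: 83%
- 0.7 within and 0.3 across: 74%
- 0.9 within and 0.3 across: 63%
- all readings of one challenge test equally correlated: 78% at 0.6 and 64% at 0.8

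Over correlations of 0.6 to 0.9 and the plausible structures, the range is roughly 56% to 85%.

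**If the times were meant to be pooled.** One test per variable per challenge, plus walk distance, NT-proBNP, KCCQ and diuretic dose, leaves 12 tests (14 with systolic and diastolic separate). That is 0.6 to 0.7 expected false positives, and a 46% to 51% chance of at least one if independent. The plan defines no pooled quantity.

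**Precision of a recovery mean.** For k readings with common correlation ρ, SD(mean) / SD(single reading) = √((1 + (k − 1)ρ) / k).

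| Assumed ρ | k = 6 (walk, step) | k = 3 (handgrip, Stroop) |
|---|---|---|
| 0.5 | √(3.5/6) = 0.76 | √(2.0/3) = 0.82 |
| 0.9 | √(5.5/6) = 0.96 | √(2.8/3) = 0.97 |

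**Comparisons after the change.** Walk 3 (distance, peak, recovery mean), step 2, handgrip 4 × 2 = 8, Stroop 4 × 2 = 8, others 3: total 24. Then 24 × 0.05 = 1.2, and 1 − 0.95^24 = 71% if independent. Fewer tests alone would not be enough; the label has to change as well.

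**The case against.** The strongest reply is that this is a small pilot and every affected endpoint is secondary or tertiary. Unadjusted analysis is acceptable in that setting, and the choice of a mean, an area or a repeated-measures model is partly preference. This stands as far as alpha adjustment goes, and none is asked for. It does not defend calling each result significant when the secondary endpoints carry no exploratory label.

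Three stronger readings are tempting, and the documents do not support them:
- **The plan commits to 50 tests.** It never says that each minute is a separate test, and the threshold appears once per between-group plan. The count depends on how the times, blood pressure and KCCQ are read, so a range is the fair statement.
- **A false positive is near certain.** Only the independent case comes close (88% to 94%), and independence is unrealistic for repeated readings in one patient.
- **A recovery mean clearly raises power.** For a 4 mm Hg difference with SD 3.4 and 10 per group, one reading has 70% power, and a mean of six has 82% to 90% at correlations of 0.7 to 0.5. But the 4 mm Hg and the correlations are not in the documents, and 3.4 is the SD for the co-primary 6-week change, not for a recovery response. At correlation 0.9 the power is 74%. If the effect fades so that it averages 2 mm Hg over recovery, power is 30% to 37% at correlations of 0.7 to 0.5, below that of one early reading at 4 mm Hg.

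**Conclusion.** The concern holds, and the remedy is cheap. On a natural reading, the plan attaches a significance claim to about 42 to 54 secondary and tertiary between-group tests, with 2.1 to 2.7 false positives expected if nothing is truly different. At least one is likely, not certain. The expected number rests on the count alone; the chance of at least one also rests on assumed correlations. If pooling over times was intended, the count falls to 12 to 14, but the text still does not say what is pooled.

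Any gain in precision from a recovery mean depends on the correlation and on the effect persisting through recovery, so it supports the change without being the main reason for it. A reader might infer that the trial's main result is compromised. It is not: the co-primary 6-week PAPm comparison is a separate single test, and the own-control and longitudinal analyses make no significance claim.

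**What to change.** 1. In the between-group plans for walk, step, handgrip, Stroop, NT-proBNP, KCCQ and diuretic dose, replace the significance sentence. Report the between-group estimate with its 95% confidence interval and a nominal p-value labelled exploratory, with no claim of significance.
2. For each challenge test and variable, pre-specify two numbers per patient as the comparisons reported: the pre-to-peak (Stroop: during-test) change, and the mean of the recovery readings. An area under the recovery curve would serve the same purpose; name one. Show individual minutes in plots only. State whether systolic and diastolic pressure are analysed separately; if so, about 24 comparisons remain.

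The cost is SAP wording. No visit, patient or alpha adjustment is added, and the pressure readings are already scheduled. There are two losses. No formal claim can be made at a single recovery minute, which the objectives do not seek. The mean is also less sensitive than an early reading if the effect fades during recovery; the separate pre-to-peak measure partly covers this.
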